## 1.0 Objectives / Specific Aims

- **Aims:** To determine if the change in brain functional connectivity after one treatment session is associated with individual patients' response to treatment
- **Hypotheses:** Change in resting state brain functional connectivity after the first session is significantly associated with gains in motor function after completion of all treatment sessions

## 2.0 Background

Stroke is a major problem for modern society, affecting more than one new US citizen every minute. Stroke is a heterogeneous disease, with high inter-subject variability associated with both baseline motor impairment and response to interventions. We have recently developed a novel intervention for post-stroke hand rehabilitation, named TheraBracelet, which uses vibrotactile sensory stimulation to increase proprioception during conventional upper extremity task-practice therapy. In our pilot study, we demonstrated a large effect size of TheraBracelet increasing upper extremity function after therapy compared to therapy alone. However, our data also show high between-subject variability in patient outcomes, an observation in line with most treatments for individuals in the chronic phase. We aim to improve efficacy of neurorehabilitation by selecting patients who are likely to recover from our specific intervention, and assigning other patients to different therapeutic programs. However, there is a lack of tools to predict whether a specific subject will benefit from a specific treatment.

## 3.0 Intervention to be studied (if applicable)

Intervention is standard occupational therapy (i.e., subjects try activities of daily living with their hand and arm such as trying to open a jar) while the person wears a TheraBracelet device. The therapy is 1-2 hours/session, 3 sessions/week for 6 weeks.

Device: A stand-alone prototype is composed of an MP3-playing watch and a vibrator (see the pictures below; total weight 40g, watch=3.7cm×5.3cm). Both items are off-the-shelf products (i.e. available to purchase for anyone). The vibrator is attached to the wristband of the watch. The vibrator's wire is connected to the MP3 player via an audio jack. The MP3 player drives the vibrator with its internal battery for at least 22 hours, enabling a full day of use after an overnight charge. The MP3 player/watch is charged using a conventional phone charger. The vibrator is a general-purpose vibrator, not specifically designed for any particular purpose. The MP3 player will play white noise vibratory signal at the intensity that is 40% below the sensory threshold (i.e. subthreshold, imperceptible to the participant). Currently there is no vibration exposure guideline for this small level of vibration. People are exposed to higher-intensity, suprathreshold vibration daily (e.g. from a phone, riding a car).

FDA: Use of this device for this protocol has been determined as non-significant risk (NSR) and exempted from IDE by the FDA (please see the enclosed letter from the FDA).

## 5.0 Inclusion and Exclusion Criteria/ Study Population

Individuals will be screened for eligibility using clinical assessments, including Fugl-Meyer Assessment of Sensorimotor Function and Monofilament Test, that will determine upper limb motor impairment and sensory deficits.

### Inclusion Criteria

- Age = 18 or older
- At least 6 months post-stroke
- Moderate upper limb impairment with the ability to participate in hand task practices
- Fingertip touch sensory deficits (e.g., Monofilament>2.83, 2-point discrimination>5mm, sense of numbness, tingling)

### Exclusion Criteria

- Complete upper limb deafferentation
- Rigidity (Modified Ashworth Scale=5)
- Botulinum toxin injection within 3 months prior to enrollment or during enrollment
- Brainstem stroke
- Comorbidity (peripheral neuropathy, orthopaedic conditions in the hand that limit ranges of motion, premorbid neurologic conditions, compromised skin integrity of the hand/wrist due to long-term use of blood thinners)
- Concurrent upper extremity rehabilitation therapy
- Language barrier or cognitive impairment that precludes following instructions or providing consent
- MRI incompatible.
- Screening: Eligibility will be determined based on the potential participant's verbal disclosure.
- Inclusion of Women and Minorities: We will include chronic stroke survivors of all genders and all racial and/or ethnic groups that are representative of the demographics of Americans who had a stroke. We will not exclude people based on sex/gender, racial or ethnic group. Specifically, according to data from the 2013 Behavioral Risk Factor Surveillance System, BRFSS (CDC), 2.7% of men and 2.7% of women  $\geq$  18 years of age had a history of stroke. Thus, approximately the same number of women and men will be recruited for this study. Also, according to the same data, 2.5% of non-Hispanic whites, 4.0% of non-Hispanic blacks, 1.3% of Asian/Pacific Islanders, 2.3% of Hispanics of any race, 4.6% of American Indian/Alaska Natives, and 4.6% of other races or multiracial people had a history of stroke. Thus, considering the stroke prevalence in each racial and ethnic group from the BRFSS together with the racial and

ethnic distribution of the American population from the 2010 U.S. Census, we will target enrollment of stroke survivors of all racial and ethnic groups accordingly.

- Exclusion of Children: We will recruit individuals who have had a stroke at least 6 months ago, who are 18 years old or older. Children under the age of 18 years will be excluded. The rationale for exclusion of children is that stroke predominantly occurs in adults, and stroke is very rare in children.

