For the MRI, all participant receiving MRI are required to complete a screening questionnaire to ensure that the person does not have any loose metal objects such as earrings or nose rings or a piece of metal in the body such as a fragment in the eye, aneurysm clips, ear implants, spinal nerve stimulators, a pacemaker, or an implant electrical device. Persons with potential for pregnancy will be excluded. Each person

will be screened before each MRI assessment. To prevent hearing loss, the participant will be asked to wear earplugs and headphones for MRI.

Potential risks that may be associated with use of wrist vibration (wrist skin irritation, increased upper limb pain, increased spasticity, weakened grip strength, worsening of hand sensation, and worsening of hand dexterity) will be systematically assessed at all times (for evaluation time points including after each week of continuous therapy and 1-month follow-up, as compared to baseline) as safety data. Negative changes in these safety measures will be communicated to the participant immediately and be explained. In addition, any other adverse events regardless of whether it is related to the device or not will be explicitly asked and recorded at all evaluation time points as well as any time they occur. All of these safety data and adverse event information, in addition to the daily safety screening and fatigue/pain monitoring data, will be reported to the DSMB, IRB, clinicaltrials.gov, and in publications.

Participants will be notified if we learn anything that might make them change their mind about participating in the study. Participants will be informed that they can drop out of the study at any time without penalty.

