Function, Box and Block, and Action Research Arm scores) are assessed after each week of therapy and at 1-month follow-up, compared to baseline. In addition to the hand function scores, broad aspects of safety will be systematically assessed at all evaluation time points for all participants as part of clinical assessments. These safety data will include any wrist skin irritation (verbal report and/or visual examination), increased upper limb pain level (on a visual analog pain rating scale from 1 to 10), increased spasticity (on the Modified Ashworth Scale), weakened grip strength (using Jamar grip dynamometer), and worsening of hand sensation (using the Semmes-Weinstein Monofilament Test score), compared to baseline. Decline will be considered as an adverse event if a reasonable criterion is met: if the participant exhibits wrist skin irritation that did not exist prior to the intervention, if the pain level increases by more than 2 points, if the Modified Ashworth Scale increases by more than 1 level (equivalent to the effect size of botulinum toxin A), if grip strength declines by more than 20% from the baseline which is approximately 2 standard deviation of the population data, if the Monofilament Test declines by one category (e.g. “normal” to “diminished light touch”) with a change of more than two points, and/or if the hand function scores decline by more than the larger of the minimum detectable change and the minimal clinically meaningful difference reported in literature. Negative changes in these measures will be communicated to the participant immediately and be explained. A potential need for medical attention will be discussed.

Any adverse events, regardless of whether it is related to the device or not, will also be explicitly asked and recorded at all evaluation time points. These safety assessments will add additional 10 minutes to the clinical assessment at each evaluation time point.

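### Wrist skin irritation is monitored against baseline but counts as an adverse event only if new, so worsening of irritation present at entry has no defined adverse-event classification

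*Combined protocol and SAP*

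**What the plan says.** **Eligibility.** The only skin item among the exclusions in section 5.0 is "compromised skin integrity of the hand/wrist due to long-term use of blood thinners". It stands in a bracketed list of comorbidities that is not marked as examples, whereas the inclusion criterion on sensory deficits is. On how these criteria are checked, the same section says: "Eligibility will be determined based on the potential participant's verbal disclosure". The screening assessments it names concern motor impairment and sensation, not skin.

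**Risk.** Section 10.0 puts skin first among the device risks to be tracked: "Potential risks that may be associated with use of wrist vibration (wrist skin irritation, increased upper limb pain" and so on. Section 14.0 also lists skin irritation, both from wearing the wristband and from prolonged vibration.

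**Data collected.** Section 12.0 has skin assessed at all evaluation time points against baseline: "These safety data will include any wrist skin irritation (verbal report and/or visual examination").

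**Adverse-event rule.** Section 12.0 then sets a criterion for each measure. For skin, a decline is an adverse event "if the participant exhibits wrist skin irritation that did not exist prior to the intervention". For pain, it is one "if the pain level increases by more than 2 points".

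**General question.** Section 12.0 adds that any adverse event, "regardless of whether it is related to the device or not, will also be explicitly asked and recorded at all evaluation time points". Section 10.0 has a similar provision: "any other adverse events regardless of whether it is related to the device or not will be explicitly asked and recorded".

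**The concern.** The rule for collecting skin data and the rule for classifying it do not match. Collection compares each visit with baseline, so worsening can be seen. Classification asks only whether the irritation is new. A participant who starts with some wrist irritation, and whose skin deteriorates under the band, shows the kind of change the monitoring is meant to detect, yet does not satisfy the criterion written for it.

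At stake is the adverse-event label and what follows from it. Under section 12.0 the label prompts early DSMB review, prompt IRB reporting, and coding by frequency, severity and relatedness. For a named device risk, those steps should not turn on whether the participant had any irritation at the start.

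**Working it through.** No figure in the plan bears on this point, so the check is a comparison of the texts.

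**Step 1. The criteria in section 12.0, side by side.**

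| Measure | Counts as an adverse event when | Covers worsening of a problem present at entry? |
|---|---|---|
| Wrist skin irritation | it is new since the intervention | No |
| Upper limb pain | rise of more than 2 points | Yes |
| Modified Ashworth Scale | rise of more than 1 level | Yes |
| Grip strength | fall of more than 20% | Yes |
| Monofilament | loss of one category with a change of more than two points | Yes |
| Hand function scores | fall beyond the larger of the detectable and the meaningful change | Yes |

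Five of the six criteria are changes from baseline. Skin alone is defined by onset.

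**Step 2. Can anyone enter with irritated or compromised wrist skin?** Yes, as written. Blood-thinner use is the only cause named, no other criterion covers skin, and no skin check is listed for screening.

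**Step 3. Follow one such participant whose irritation worsens during the six weeks of therapy.**

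- *Seen?* Yes. Skin is assessed after each week of therapy and at the 1-month follow-up, against baseline (sections 10.0 and 12.0).
- *Told to the participant?* Yes. Negative changes are communicated immediately, whether or not a criterion is met.
- *Tabulated and reported as safety data?* Yes. Section 12.0 tabulates safety data at each time point. Section 10.0 sends them, with the adverse events, to the DSMB, the IRB, ClinicalTrials.gov and publications.
- *Meets the skin criterion?* No. The irritation existed before the intervention.
- *Prompt DSMB notice?* Not assured. Section 12.0 has the DSMB convene at the end of the study unless an adverse event occurs.
- *IRB notice as it occurs?* Not assured. Section 12.0 attaches this to adverse events.
- *In the MedDRA summary?* Not assured. That summary is of adverse events.

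**Step 4. Does the general question close the gap?** It may. Staff ask about adverse events explicitly, so the participant need not raise the matter unprompted. But section 10.0 speaks of other adverse events, which can be read as those outside the listed measures. Staff who apply the explicit skin rule could reasonably record no adverse event.

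**Step 5. Size.** The documents give no prevalence of wrist skin irritation, so the expected number of affected participants cannot be computed. One such person would be 1/8 = 12.5% of planned recruits, or 1/4 = 25% of the four targeted completers. These fractions restate the sample size. They do not estimate a bias.

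**The case against.** The strongest reply is that nothing is hidden. Skin is examined or asked about at every evaluation, negative changes are explained, the data are tabulated, the DSMB sees individual participants' data, and adverse events are explicitly sought. Irritation that raises upper limb pain by more than 2 points would also meet the pain criterion. This reply stands. A reader might infer from the new-onset wording that worsening goes uncounted altogether, or that the skin safety result is biased toward no events. The documents do not support either inference. Only the adverse-event classification is open.

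A second reply is that limiting the exclusion to one cause is a clinical choice. The documents call the skin risk minor, describe a 40 g device with subthreshold vibration that the FDA treated as non-significant risk, and provide for adjusting or replacing the wristband. This also stands, in that a reader might conclude that the exclusion is wrong, and the documents do not establish that. They show only that the cause limit is unexplained beside a named skin risk.

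A third reply is that this is an eight-person pilot and the matter touches no efficacy endpoint. That is true and limits its weight. It does not remove the mismatch between two rules in the same section.

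**Conclusion.** The point holds for classification. In section 12.0, wrist skin irritation is the only listed measure for which worsening of a problem present at entry cannot meet the adverse-event criterion, although the same section collects skin data against baseline. Such worsening would appear in the safety tables. It may be absent from the adverse-event count, immediate DSMB notice, prompt IRB reporting and the MedDRA summary, depending on how staff use the general question.

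The number of participants affected is unknown and could be zero. The conclusion rests on two readings: that the comorbidity list in section 5.0 is closed, and that staff apply the skin criterion as written. It does not extend to a claim that skin safety goes unmonitored, or to any judgement on which eligibility rule is clinically right. The correction to section 12.0 is worth making because the rule is explicit and the change is small.

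**What to change.** 1. In section 12.0, define the skin criterion as irritation that is new or worse than at baseline, in line with the measures beside it.
2. Record a visual examination of the wrist skin for every participant at baseline and at each evaluation. The present wording allows verbal report alone, so a visual baseline is not guaranteed. No grading scale is given for skin, so the sponsor should also state how the examiner will judge worsening.
3. Reconcile the cause-limited skin exclusion in section 5.0 with the skin irritation risk in sections 10.0 and 14.0, by justifying the limit or revising it. The choice is the sponsor's.

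**Cost.** The first change is one line of text. The second is a brief recorded check. With baseline, six weekly evaluations and one follow-up there are 1 + 6 + 1 = 8 checks per participant, so at most 8 × 8 = 64 if all eight recruits complete. Section 12.0 already allots 10 minutes per evaluation to safety assessments. The adverse-event count may rise slightly. The third needs a sentence of justification or a revised criterion.

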## **10.0 Study Design / Methods**

- Study design: A single cohort study. Describe what subjects will do. Subjects will receive 6-week standardized task-practice therapy with TheraBracelet on their affected wrist (2 hr/d, 3d/wk, 18-session). Clinical assessments will be performed at baseline, after each week of therapy, and at 1-month follow-up. Change in brain FC during rest before vs. after the first therapy session will be assessed using fMRI and EEG independently.
- Schedule: Participation in the study will last approximately 10 weeks. Participants will visit the laboratory 3 times a week for 6 weeks (18 sessions) to receive treatment. Additionally, participants will visit the laboratory for 3 assessment visits (before and after the treatment intervention and at one-month follow-up).

- MRI: MRI assessments will be performed two times, before and after the initial therapy session. The first scan will be for 1 hour. The second scan will be for 30 minutes. Subjects will rest on a scanner bed and either rest or press buttons with the fingers for the first scan while their resting or task fMRI is obtained. In addition to fMRI, structural MRI scan will be obtained for the individual participant's brain anatomy.
- EEG: For the EEG assessment, participants will wear an EEG cap on their head. Gel will be applied to individual EEG electrodes with a blunt syringe that does not penetrate the skin (taking approximately 30 min for this preparation). During the assessment, the participant will rest comfortably in a chair and either rest or grip with the fingers. The EEG assessment will take approximately 0.5 hour to complete, in addition to the 30 min prep time.

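### Does the verbal-disclosure sentence in Section 5.0 leave examiner-rated eligibility criteria undecided?

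*Combined protocol and SAP*

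**What the plan says.** Section 5.0 opens with "Individuals will be screened for eligibility using clinical assessments, including Fugl-Meyer Assessment of Sensorimotor Function and Monofilament Test" and gives those assessments the task of establishing how impaired the arm is and how much sensation is lost. The Inclusion Criteria then require "Moderate upper limb impairment with the ability to participate in hand task practices", with no score range. They also require a fingertip sensory deficit, illustrated both by test thresholds and by symptoms a patient can report. The Exclusion Criteria include "Complete upper limb deafferentation" and "Rigidity (Modified Ashworth Scale=5". A screening bullet further down that list says "Eligibility will be determined based on the potential participant's verbal disclosure".

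On timing, Section 10.0 says "Clinical assessments will be performed at baseline, after each week of therapy, and at 1-month follow-up". Its schedule bullet says "participants will visit the laboratory for 3 assessment visits (before and after the treatment intervention and at one-month follow-up". On imaging it says "MRI assessments will be performed two times, before and after the initial therapy session. The first scan will be for 1 hour". Section 12.0 lists spasticity on the Modified Ashworth Scale among the safety measures taken at every evaluation time point and compared with baseline.

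**The concern.** The disclosure sentence carries no qualifier. It is not confined to a telephone pre-screen, to history items or to MRI compatibility, and its verb is one of deciding rather than of preliminary sorting. Taken alone, it asks a participant's own account to settle matters that only an examiner can rate: whether impairment is moderate, and whether the Modified Ashworth score is 5.

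The Modified Ashworth Scale is never named as a screening test. It appears as an exclusion in Section 5.0 and as a safety measure in Section 12.0. The Fugl-Meyer is named only in the opening of Section 5.0. Staff who read only the later bullet might therefore leave an examination undone, or learn of a disqualifying score late, perhaps after the one-hour first scan.

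At stake is who enters a very small cohort. Section 6.0 recruits eight, and Section 11.0 targets complete data on four. One ineligible entrant would be 1/8 = 12.5% of those recruited or, if that person completed, 1/4 = 25% of the completers in the regression.

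**Working it through.** No sample size, power or error rate enters this point, so the check is a comparison of text. Each of the 12 listed criteria (four inclusion, eight exclusion) is set against the source the protocol offers for it.

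| Criterion | Source available in the protocol |
|---|---|
| Age; time since stroke | Participant's account |
| Botulinum toxin; brainstem stroke; comorbidity; concurrent therapy | Mainly participant's account |
| MRI incompatibility | Participant's account, plus the MRI questionnaire in Section 10.0 |
| Language or cognitive barrier | Evident in the consent conversation (Section 9.0) |
| Moderate impairment | Fugl-Meyer, opening of Section 5.0 |
| Fingertip sensory deficit | Monofilament Test, opening of Section 5.0; reported symptoms also count |
| Complete deafferentation | Sensory assessment, opening of Section 5.0 |
| Modified Ashworth score of 5 | Rated scale; baseline safety measure, Section 12.0 |

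The count is 2 + 4 + 1 = 7 criteria that rest mainly on what the participant reports, 1 that shows itself at consent, and 4 that call for examination: 7 + 1 + 4 = 12. The allocation is a reading of the text, since the protocol does not print it.

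1. *Impairment and sensation.* The opening of Section 5.0 sends both to clinical assessment and says expressly that this is for eligibility. The later bullet does not withdraw that, and it contains no word such as only or solely. A sentence that is specific about two attributes and a general sentence about eligibility can both be obeyed. This covers three of the four examination criteria.

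2. *Modified Ashworth.* An exclusion defined by a score on a rated scale presupposes that someone rates it. The list of screening tests in Section 5.0 is introduced as non-exhaustive. Section 12.0 compares later Modified Ashworth values with baseline, so a baseline value must exist. The two timing statements in Section 10.0 differ on how often assessments occur, but both place one before treatment. The score should therefore be known before the first therapy session, and it is already a listed exclusion.

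3. *Fugl-Meyer.* It is absent from the clinical assessment described in Section 10.0, which covers hand function, self-report and the acute response to vibration. A screening test needs to be prescribed only once, and Section 5.0 does so.

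4. *Order relative to the first scan.* Section 10.0 does not say whether the baseline assessment or the first scan comes first. If the scan came first and the score then excluded the person, the loss would be one scan. Someone excluded before therapy has neither a post-session connectivity change nor a treatment outcome, so cannot enter the linear regression in Section 11.0.

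**The case for a change.** The best case for a change is that eligibility defines the cohort and staff need one rule. The bullet is unqualified. Even if it is read as covering only the exclusion list in which it stands, that list contains the Modified Ashworth criterion, so the narrower reading does not rescue it. An open-ended list of tests earlier in the section does not plainly override a later flat statement, and no section says that a baseline score is checked against the exclusion. A clarification would cost a sentence or two and no new test, since the examinations are already planned. Its one drawback would be an occasional screen failure after consent.

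Part of this stands. The division between asked and examined criteria is not written down, the Modified Ashworth Scale is not named for screening, and the order of baseline assessment and first scan is not given. The harm does not follow from these gaps. A missed Fugl-Meyer requires staff to disregard the opening sentence of the same section. A Modified Ashworth score of 5 that goes unused requires them to record a listed exclusion and then ignore it. Late discovery after the scan rests on a visit order that the documents do not state. The 12.5% and 25% shares show what one wrong entry would amount to, not how likely it is.

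**Conclusion.** The concern does not call for a change. Both sentences are in the current text and nothing reconciles them explicitly, but they are compatible, and a team following the whole protocol would examine the four criteria that need examination. Writing out the allocation would record what the plan already leads staff to do. It would alter neither the analysis nor any stated figure.

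The effect on results cannot be given a number, because the documents provide no rate of wrong admission. What can be said is that 0 of the 12 criteria are left without a workable source.

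This rests on three assumptions: the two statements in Section 5.0 are meant to be read together; the baseline assessment in Section 10.0 includes the Modified Ashworth rating that Section 12.0 needs for comparison; and an exclusion found at that assessment is applied before therapy begins.
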